5.5.3.7. TtP and iTtP

TtP and iTtP are defined as the time from the first day of study treatment until the first date of radiological disease progression and will be summarized using Kaplan-Meier estimates in the efficacy population.

Patients with missing data will be censored/considered as having an event as specified in Table below.

Table 6 TtP and iTtP events and censoring

Situation	Date of progression or censoring	Outcome
Incomplete or no baseline tumor assessment.	First day of study treatment	Censored
Start of next-line anti-cancer therapy.	Date of the last tumor assessment with non-progression before the start of next-line anti-cancer therapy.	Censored
Death before the first disease progression assessment.	Date of death.	Censored
Death between adequate tumor assessment visits.	Date of death.	Censored
Death after one missed adequate tumor assessment.	Date of death.	Censored
Progression after one missed adequate tumor assessment.	Date of progression.	Progressed
Progression after more than one missed adequate tumor assessment.	Date of the last evaluable tumor assessment.	Censored
No progression.	Date of the last evaluable tumor assessment.	Censored

For iTtP, the progression date to be used for calculation should be the first date at which progression criteria are met (i.e, the date of iUPD) provided that iCPD is confirmed at the next assessment. If iUPD occurs, but is disregarded because of later iSD, iPR, or iCR, that iUPD date should not be used as the progression event date.

If progression is not confirmed and there is no subsequent iSD, iPR, or iCR, the iUPD date should still be used if:

- the patient stops protocol treatment because they were not judged to be clinically stable, or
- no further tumor assessments are done, or
- the next timepoint responses are all iUPD, and iCPD never occurs, or
- the patient dies from his cancer.

TtP according to RECIST and iRECIST will be listed for ASaT population.

TtP according to RECIST and iRECIST will be displayed graphically using Kaplan-meier plots for efficacy and ASaT populations including count for numbers of patients at risk.

5.5.4. Sensitivity Analyses for the Secondary Efficacy Analysis

Secondary efficacy analysis will be repeated for ASaT population.

5.5.5. Subgroup Analysis

Not Applicable

5.5.6. Exploratory Analysis

5.5.6.1. PFS2

PFS2 is defined as the time from the first day of study treatment until the date of second disease progression (i.e., progression on next-line anti-cancer treatment) or death and will be summarized using Kaplan-Meier estimates in the ASaT population. Patients with missing data (i.e., without second radiological disease progression) will be censored at the last time known to be alive.

PFS2 data will be listed for ASaT population.

PFS2 will be presented graphically using Kaplan-Meier plots for ASaT population.

5.5.6.2. OS

OS is defined as the time from the first day of study treatment until the date of death and will be summarized using Kaplan-Meier estimates in the ASaT population.

Patients with missing data will be censored at the last date known to be alive. The last known date to be alive will be derived for patients at the analysis cutoff using the latest complete date among the following:

- Patient assessment dates (blood draws [laboratory, PK], vital signs, ECOG performance status, ECG, tumor assessments, tumor measurement, or tumor biopsy dates)
- Start and end dates of anti-cancer therapies administered after study treatment discontinuation
- AE start and end dates
- Concomitant medication start and end dates
- Concurrent procedure date
- Date of death collected on the ‘Death Details’ electronic Case Report Form (eCRF)
- Date of last contact collected on the ‘Survival Status’ eCRF where status is ‘alive’; or date last known to be alive if status is ‘unknown’
- Study treatment start and end dates
- Date of discontinuation on disposition eCRF pages (do not use if reason for discontinuation is lost to follow-up).

Only dates associated with actual contact of the patient will be used in the derivation. Dates associated with a technical operation unrelated to patient status such as the date a blood sample was processed will not be used. Assessment dates after the cutoff date will not be applied to derive the last contact date, if applicable.

OS data will be listed for ASaT population.

OS will be presented graphically using Kaplan-Meier plots ASaT population.

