Serum for cytokines		X ¹⁹						X ^{19,20}						
Whole blood for exploratory biomarkers		X ^{11,21}						X ¹¹						
Survival status														X ²²
Next-line anti-cancer treatment														X ²²
Date of progression on next-line anti-cancer treatment														X

- * Criteria for discontinuation of study interventions are listed in section [7.1](#).
- ** Every 30 (± 2) days until 60 (± 2) days after the last dose of cetuximab or 30 (± 2) days after the last dose of nanrilkefusp alfa, whichever is later
- 1. No study-specific procedures are to be performed before Informed Consent Form signature
- 2. Age at screening and gender
- 3. Primary tumor location, histology/cytology, initial diagnosis date, lines of previous treatment, start and stop dates of the treatments before this study, any prior mutations/genetic analysis (e.g., EGFR, K-RAS/N-RAS mutations), and the date of the latest disease progression if not coinciding with the stop date
- 4. Within 7 days before day 1 of cycle 1
- 5. On the day of dosing before nanrilkefusp alfa administration and/or cetuximab administration
- 6. Sample can be taken within 24 hours before nanrilkefusp alfa and/or cetuximab administration
- 7. Before nanrilkefusp alfa administration and afterwards as clinically required
- 8. Follow-up visit 30 (± 2) days after the last dose of nanrilkefusp alfa and/or cetuximab (whichever occurs later)
- 9. Last body weight assessment within 3 days prior to day 1 should be used for dose calculation.
- 10. Before and after nanrilkefusp alfa administration as described in section [8.2.3](#)
- 11. Before nanrilkefusp alfa and/or cetuximab administration
- 12. Additional samples may be taken as clinically indicated
- 13. Before nanrilkefusp alfa administration and 2 hours (± 15 min) after nanrilkefusp alfa administration
- 14. Tumor scans performed as part of routine clinical management are acceptable for screening if they are of acceptable diagnostic quality and performed within 21 days prior to ICF signature
- 15. Time to be recorded
- 16. Time to be recorded; on day 1 and day 8, cetuximab infusion will start within 30 minutes after nanrilkefusp alfa administration
- 17. Contact 90 (± 2) days after the last dose of nanrilkefusp alfa and/or cetuximab (whichever occurs later)
- 18. To be collected up to cycle 4
- 19. Before nanrilkefusp alfa administration and 6 hours (± 15 min) after nanrilkefusp alfa administration
- 20. Only in cycle 2

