8.1.3 End of treatment and follow-up tumor imaging

If patients discontinue study interventions, tumor scans should be performed at the time of discontinuation (± 4 -week window) unless previous scans were obtained within 4 weeks of discontinuation.

If patients discontinue study interventions without documented disease progression, every effort should be made to monitor disease status by acquiring tumor scans using the same schedule used while on treatment (every 6 weeks [± 2 weeks]).

Scans are to be continued until:

- Confirmed disease progression per iRECIST

- Start of next-line anti-cancer treatment
- Pregnancy of the patient
- Withdrawal of consent by the patient
- End of the study

All imaging assessments need to have confirmatory imaging using the identical method after at least 4 weeks.

Patients who are clinically stable and treated past radiographic progression may continue to be assessed until progression is confirmed according to the rules of iRECIST, when clinically appropriate.

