9.3.4 Exploratory endpoint analysis

- PFS on next-line anti-cancer treatment (PFS2)

PFS2 is defined as the time from the first day of study treatment until the date of second radiological disease progression (i.e., progression on next-line anti-cancer treatment) or death and will be summarized using Kaplan-Meier estimates.

Patients with missing data (i.e., without second radiological disease progression) will be censored at the last time known to be alive.

- OS

OS is defined as the time from the first day of study treatment until the date of death and will be summarized using Kaplan-Meier estimates. Patients with missing data will be censored at the last time known to be alive.

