5.5.3.5. PFS and iPFS

PFS and iPFS are defined as the time from the first day of study treatment until the first date of radiological disease progression or death and will be summarized using Kaplan-Meier estimates in the efficacy population.

Patients with missing data will be censored/considered as having an event as specified in the table below.

Table 5 PFS and iPFS events and censoring

Situation	Date of progression or censoring	Outcome
Incomplete or no baseline tumor assessment.	First day of study treatment	Censored

Start of next-line anti-cancer therapy.	Date of the last tumor assessment with non-progression before the start of next-line anti-cancer therapy.	Censored
Death before the first disease progression assessment.	Date of death.	Progressed
Death between adequate tumor assessment visits.	Date of death.	Progressed
Progression or death after one missed adequate tumor assessment.	Date of progression or death, whichever is earliest (if both occur).	Progressed
Progression or death after more than one missed adequate tumor assessment.	Date of the last evaluable tumor assessment.	Censored
No progression, no death.	Date of the last evaluable tumor assessment.	Censored

For iPFS, the progression date to be used for calculation should be the first date at which progression criteria are met (i.e, the date of iUPD) provided that iCPD is confirmed at the next assessment. If iUPD occurs, but is disregarded because of later iSD, iPR, or iCR, that iUPD date should not be used as the progression event date.

If progression is not confirmed and there is no subsequent iSD, iPR, or iCR, the iUPD date should still be used if:

- the patient stops protocol treatment because they were not judged to be clinically stable, or
- no further tumor assessments are done, or
- the next timepoint responses are all iUPD, and iCPD never occurs, or
- the patient dies from his cancer.

PFS according to RECIST and iRECIST will be listed for ASaT population.

PFS according to RECIST and iRECIST will be displayed graphically using Kaplan-meier plots for efficacy and ASaT populations including count for numbers of patients at risk.

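### PFS2 is censored at the date last known alive, so a patient whose second progression goes unrecorded contributes overall survival instead; separately, the SAP's event and censoring wording disagree on clinical progression

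*SAP*

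**What the plan says.** PFS2 is an exploratory endpoint, summarised by Kaplan-Meier without a test.

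- **Event, protocol 9.3.4:** time from first treatment "until the date of second radiological disease progression (i.e., progression on next-line anti-cancer treatment) or death".
- **Event, SAP 5.5.6.1:** time from first treatment "until the date of second disease progression (i.e., progression on next-line anti-cancer treatment) or death". The radiological condition is gone.
- **Censoring, both documents:** "Patients with missing data (i.e., without second radiological disease progression) will be censored at the last time known to be alive".
- **OS censoring, SAP 5.5.6.2:** "Patients with missing data will be censored at the last date known to be alive". The list of sources for that date includes items that say nothing about tumour status, such as "Concomitant medication start and end dates".
- **First-progression PFS, for contrast, SAP 5.5.3.5:** a patient without progression or death is censored at "Date of the last evaluable tumor assessment".
- **Data collection:** under protocol 8.1.3, one of the points at which study scans end is "Start of next-line anti-cancer treatment". Second progression then rests on a row of the schedule in protocol 1.3, "Date of progression on next-line anti-cancer treatment", marked in the follow-up column. The rows for survival status and next-line treatment carry note 22 (day 90, then every 3 months). This row carries no note.

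SAP section 6 lists three departures from the protocol: stable-disease derivation, duration of follow-up and PK parameters. PFS2 is not among them. SAP 4.2.1 refers the reader to section 5.5.3 for PFS2 censoring, but that section has no PFS2 rule.

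**The concern.** Censoring should fall at the last date on which the patient was known to be free of the event. For PFS2 that means alive and without second progression. A patient on next-line therapy can be known alive from a phone contact or a medication record while nobody has established whether the tumour has progressed again. The plan leaves that patient in the risk set as event-free up to the last survival contact, and counts the death, if it comes, as a late PFS2 event. Both push the curve upward, and the trial has no control arm against which an inflated PFS2 would show.

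The second matter is one of definition. A patient who progresses clinically on next-line therapy, without a scan, is an event under the SAP's first sentence and censored under its second. Two programmers could build different PFS2 datasets from the same text.

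**Working it through.** **Step 1: compare the rules.** No assumption is needed. Take a patient with no recorded second progression.

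| Patient's state | PFS2 under the plan | OS under the plan |
|---|---|---|
| Died | Event at death | Event at death |
| Alive | Censored when last known alive | Censored when last known alive |

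The two columns are identical. If no second progression were recorded for anyone, the PFS2 curve would be the OS curve. If every one were recorded, there would be no bias.

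**Step 2: illustrate the size.** The documents give no PFS2 median, event count or capture rate, so there is no planned figure to reproduce. Every input here is an assumption:

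- exponential times with a median of 4 months each for start to first progression, first to second progression, and second progression to death;
- a share u of patients (10, 20 or 30%) whose second progression is never ascertained, and who are last known free of it at first progression (a stand-in for the start of next-line therapy);
- cut-off uniform over 12-36 months, or over 4-14 months for an early cut-off, independent of outcome.

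Each stage has mean 4/ln 2 = 5.771 months. True PFS2 is the sum of two stages, with median 1.678 × 5.771 = 9.7 months. OS is the sum of three, with median 2.674 × 5.771 = 15.4 months.

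Under the plan, the Kaplan-Meier curve estimates a mixture of the two: (1 − u) × S(PFS2) + u × S(OS). With x = t/5.771 the median solves

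e^(−x) × (1 + x + u·x²/2) = 0.5.

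For u = 0.2, t = 10.71 gives x = 1.856, and 0.1563 × (1 + 1.856 + 0.1 × 3.445) = 0.500. The planned median is therefore about 10.7 months, and it does not depend on the length of follow-up.

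Re-censoring moves living patients without ascertained second progression back to the last date known free of it and leaves deaths as events. Simulated medians in months, good to about 0.1:

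| Not ascertained | True | Plan, either follow-up | Re-censored, 12-36 months | Re-censored, 4-14 months |
|---|---|---|---|---|
| 10% | 9.7 | 10.2 | 10.1 | 9.8 |
| 20% | 9.7 | 10.7 | 10.5 | 9.9 |
| 30% | 9.7 | 11.3 | 10.9 | 10.0 |

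**Step 3: what re-censoring removes.** The plan's bias is 0.5, 1.0 and 1.6 months. With 12-36 months of follow-up, re-censoring takes off 0.1, 0.2 and 0.4. With 4-14 months it takes off 0.4, 0.8 and 1.3. The difference lies in deaths: with long follow-up most patients with an unrecorded second progression have died, and their deaths still count as late events.

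**Step 4: the wording.** Clinical progression on next-line therapy satisfies the SAP event and also the SAP condition for being censored. If the event sentence governs, the endpoint differs from the protocol's and section 6 should say so. If the censoring sentence governs, the endpoint is the protocol's and the event sentence is wrong.

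**The case against.** Several points on the other side have force.

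- **Low stakes.** PFS2 is exploratory, untested and listed patient by patient. This stands. A reader might infer that the trial's main conclusions are at risk. They are not, because PFS2 does not enter ORR, the sample size or futility.
- **Capture may be good.** The second-progression row is marked in follow-up, and next-line treatment is asked about every 3 months. A reader might infer from the missing note that second progression will go unasked. The documents do not show that; they only fail to require a timing. The 10-30% shares are assumptions.
- **Some patients are correctly handled.** PFS2 needs progression on next-line treatment, so a patient known alive and not on next-line therapy is free of progression on such treatment at that contact. For this group the date last known alive is the right anchor.
- **Planned follow-up is long.** Protocol 4.4 ends the study one year after the last patient's last dose or 3 years after the last patient's first dose, whichever is earlier. A patient followed to that point has at least 12 months, so the 12-36 month column is nearer the plan. The 4-14 month column applies to an early cut-off or an early stop.
- **Sampling error is larger.** On the same assumptions with 52 patients, 20% unascertained and 12-36 months of follow-up, the planned median has a 95% sampling range of about 8.2 to 13.6 months. A shift of 0.2 from re-censoring is small beside that, though it is systematic and always in one direction.

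A reader might also infer that the wording conflict itself drives PFS2 toward OS. It does not: under the event sentence clinical progression counts and nothing drifts. It is a separate drafting fault.

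**Conclusion.** The censoring rule is wrong as written in both documents. A patient with an unrecorded second progression contributes OS to PFS2, and the bias is upward. That follows from the text alone. The size does not: on the assumptions above it is about 0.5 to 1.6 months on a true median of 9.7, and it vanishes with complete capture.

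It would be too strong to say that a new censoring date cures this. At 12-36 months of follow-up it removes 0.1 to 0.4 months. It gains less again if progression status is known more recently than first progression: in a variant with 4-14 months of follow-up, where only patients with a missed second progression were re-censored, at a random earlier date, the medians were 10.0, 10.4 and 10.7. Better capture is what removes the rest.

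The mismatch between the SAP's event and censoring wording is a real but separate inconsistency, not declared in section 6.

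**What to change.** 1. In SAP 5.5.6.1, and in protocol 9.3.4 at the next amendment, censor PFS2 at the last date the patient is known to be alive and without second progression. For patients known not to have started next-line therapy, that is the last contact.
2. Use one definition of second progression in the event and censoring sentences: either radiological, as in the protocol, or progression by any documented means. Declare any departure from the protocol in SAP section 6, and correct the cross-reference in SAP 4.2.1.
3. Apply note 22 of the schedule to the second-progression row, so that status is recorded at each 3-monthly contact. This does most to limit deaths after unrecorded progression.

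Censoring every such death is not a safe substitute. In a simulation with assumed medians of 4, 3 and 4 months (true PFS2 8.4, OS 14.1), 20% capture and 12-36 months of follow-up, it gave a median PFS2 of 17.3 months, longer than OS.

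The cost is one sentence in each document, a footnote in a protocol amendment and one question at an existing contact. Protocol 10.1.1 sends amendments to ethics committees and competent authorities unless they are only logistical or administrative, so the protocol changes are best carried with the next amendment. The reported PFS2 may be slightly shorter.

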5.5.6.3. Duration of Follow up

A reverse Kaplan-Meier analysis will be performed on OS in the ASaT population to estimate the median follow-up incorporating censoring rules and flipping event/censored events.

Duration of Follow up data will be listed for ASaT population.

Duration of Follow up will be presented graphically using Kaplan-Meier plots ASaT population.

5.5.6.4. Assessment of the EGFR mutational status at baseline and at disease progression

EGFR mutational status will be listed for ASaT population.

5.5.6.5. Tumor Burden Analysis

Absolute change from baseline and percent change from baseline for sum of target and new lesion diameters will be summarized in the efficacy population using descriptive statistics for each week of tumor assessment. The best percent change of sum of target and new target lesion will be presented in summary tables.

A waterfall plot of maximum percent reduction in the sum of diameter of target lesions from baseline will be created in the efficacy population. These plots will display the best percentage CFB in the sum of the diameter of all target lesions for each patient.

A spaghetti plot of percent reduction in the sum of target lesions from baseline will be created in the efficacy population to plot the change in tumor burden over time (in weeks from start of treatment) for each patient.

Best percent change from baseline for sum of target lesion diameters is defined as the lowest (minimum) percent change from baseline and will be calculated with one decimal place.

Sum of target lesion diameters will be listed for enrolled population.

5.6. Safety

5.6.1. Extent of Exposure and Compliance

Exposure/Compliance	nanrilkefusp alfa	Cetuximab
Cycle Started	Patient received at least one dose of nanrilkefusp alfa in that cycle	Patient received at least one dose of cetuximab in that cycle
Cycle started in combination therapy is defined as patient receiving at least one dose of nanrilkefusp alfa and cetuximab in that cycle.		
Completed cycle	Patient received 4 doses of nanrilkefusp alfa and 3 doses of cetuximab in that cycle, or patient started the next cycle.	

Duration of cycle (days)	The day prior to the date of cycle start (day 1 in each cycle) will be considered as the end of the previous cycle. For the last cycle, 21 days will be used.	

Duration of exposure (days)	Last dose date – Start dose date + 1	Last dose date – Start dose date + 1
	Last dose date of either nanrilkefusp alfa or cetuximab, whichever is later – Start dose date of nanrilkefusp alfa or cetuximab, whichever is earlier + 1	

Real dose administered	(2 x Total volume administered) / patient weight (µg/kg)	Actual dose per administration / BSA (mg/m ²)

Actual cumulative dose	Sum of the real doses (µg/kg) administered	Sum of the real doses (mg/m ²) administered

Duration of exposure (days) for completed cycles (*)	Considering only completed cycles: End date of last completed cycle – Start dose date of nanrilkefusp alfa or cetuximab, whichever is earlier + 1	

Exposure/Compliance	nanrilkefusp alfa	Cetuximab
Actual dose intensity (*)	Considering only completed cycles: Actual cumulative dose / Duration of exposure for completed cycles (days) in (μ g/kg/day)	Considering only completed cycles: Actual cumulative dose / Duration of exposure for completed cycles (days) in ($mg/m^2/day$)
Actual dose intensity by cycle (*)	Considering only completed cycles: Actual cumulative dose in that cycle / Duration of cycle (days) in (μ g/kg/day)	Considering only completed cycles: Actual cumulative dose in that cycle / Duration of cycle (days) in ($mg/m^2/day$)
Intended dose intensity	(Initial dose of nanrilkefusp alfa * 4 doses)/ 21 day	(As per protocol initial dosing)/ 21 day Protocol initial dosing : 900 mg/m^2 of BSA for cycle 1 750 mg/m^2 of BSA for subsequent cycles
Relative dose intensity by cycle (%) (*)	Considering only completed cycles: 100 * (Actual dose intensity by cycle / Intended dose intensity)	Considering only completed cycles: 100 * (Actual dose intensity by cycle / Intended dose intensity)
Overall relative dose intensity (%) (*)	Considering only completed cycles: 100 * (Actual dose intensity / Intended dose intensity)	Considering only completed cycles: 100 * (Actual dose intensity / Intended dose intensity)
Compliance with planned dose (%)	100 * (Real dose administered / Planned dose) at each dosing, taking into account per protocol dose changes	100 * (Real dose administered / Planned dose) at each dosing, taking into account per protocol dose changes

(*) only completed cycle as defined should be considered for derivation.

Descriptive statistics in the ASaT population and Efficacy population will be provided for:

- Total number of cycles started
- Total number of doses administered as well as the frequency of patients with 1, 2, 3, 4, 5, 6, 7, 8, or ≥ 9 injections.
- Duration of exposure
- Number of patients with at least one dose adjustment
- Actual cumulative dose
- Actual dose intensity
- Overall relative dose intensity

For the combination therapy, the total number of cycles started and the duration of exposure will be summarized.

Treatment compliance will be listed together with exposure for the ASaT population. Missing data will not be imputed and only original data for those fields (for example, date fields) will be presented in the listing together with derived variables such as the calculated compliance (%) and exposure duration.

Further, study treatment administration/infusion data (including total volume administered and dose adjustments, etc.) will be listed for the ASaT population.

Mean of Relative Dose Intensity by Cycle will be presented graphically for ASaT population using bar chart.

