Patients in the initial 9 µg/kg safety cohort may also have a dose increase to 12 µg/kg nanrilkefusp alfa in the next treatment cycle at the discretion of the investigator if there are no safety concerns in the 12 µg/kg safety cohort.

Patients in the safety cohorts who do not fulfill the DLT evaluability criteria (see section [4.1.3](#)) for any reason other than DLT during the DLT assessment period will be replaced until at least 3 patients per cohort have completed their DLT assessment period.

In the main cohort of the study, patients will be treated with nanrilefusp alfa in combination with cetuximab in 21-day cycles. An independent data monitoring committee (IDMC) will be established to review safety and efficacy data at certain time intervals, or when the interim analysis for futility is triggered, once the main cohort of the study starts.

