9.5 Sample size determination

In the safety cohorts, the traditional 3+3 design dose escalation will be applied. Therefore, 3 to 6 DLT-evaluable patients per dose level will be included in a cohort. The estimated number of patients is 6-12.

The overall sample determined in this trial is 52 patients in efficacy population (see section 9.2.3) which includes patients from the safety cohorts and the main cohort.

The total sample size is based on a Bayesian calculation: Markov chain Monte Carlo has been used for the sample size determination. Assuming a desired ORR for the number of responses, and a uniform prior distribution between 0 and 1, the sample size of 52 patients will ensure at least 80% posterior probability to achieve an effect above the minimal ORR:

- Benchmark ORR: 20%²¹
- Minimal ORR (relative increase, absolute increase): 28.8% (1.44, 8.8%)
- Desired ORR (relative increase, absolute increase): 36.8% (1.84, 16.8%)

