If there are no safety concerns in the 12 µg/kg safety cohort, the study will proceed to the main cohort and recruit patients who will receive 12 µg/kg nanrilefusp alfa in combination with cetuximab.

Patients in the initial 9 µg/kg safety cohort may also have a dose increase to 12 µg/kg nanrilefusp alfa in the next treatment cycle at the discretion of the investigator if there are no safety concerns in the 12 µg/kg safety cohort.

Patients in the safety cohorts who do not fulfill the DLT evaluability criteria for any reason other than DLT during the DLT assessment period will be replaced until at least 3 patients per cohort have completed their DLT assessment period.

In the main cohort of the study patients will be treated with nanrilkefusp alfa in combination with cetuximab in 21-day cycles as described in the study protocol. An Independent Data Monitoring Committee (IDMC) will be established to review safety and efficacy data at certain time intervals, or when the interim analysis for futility is triggered, once the main cohort of the study starts.

Study periods

Participation of each patient will consist of the below study periods.

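### SAP 5.6.1 can overstate overall relative dose intensity: it drops an interrupted last cycle and keeps the initial nanrilkefusp alfa dose as target after escalation. It also gives no overall cetuximab target.

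*SAP*

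**What the plan says.** SAP 5.6.1 defines a completed cycle as "Patient received 4 doses of nanrilkefusp alfa and 3 doses of cetuximab in that cycle, or patient started the next cycle". Actual dose intensity and relative dose intensity, by cycle and overall, are restricted to such cycles, and a footnote repeats that "only completed cycle as defined should be considered for derivation". A patient's last cycle is given a length of 21 days.

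The intended nanrilkefusp alfa intensity is "Initial dose of nanrilkefusp alfa * 4 doses)/ 21 day". For cetuximab the intended dose is 900 mg/m² in cycle 1 and 750 mg/m² in each later cycle, each divided by 21 days. The overall figure for either drug is "100 * (Actual dose intensity / Intended dose intensity", with one denominator.

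Protocol 4.1.1 covers escalation of those who began at 9 µg/kg in the first safety cohort: they "may also have a dose increase to 12 µg/kg nanrilkefusp alfa in the next treatment cycle at the discretion of the investigator", provided the 12 µg/kg cohort raises no safety concern. SAP 2.1 repeats this. Overall relative dose intensity is to be summarised for both the ASaT and the Efficacy populations.

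**The concern.** Relative dose intensity should show how much of the planned treatment was delivered. Three features of the definition work against that.

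- The completed-cycle rule is asymmetric. An interrupted cycle counts if another follows, but the cycle in which treatment ends counts only if all doses of both drugs were given. Under Protocol 7.1, stopping nanrilkefusp alfa also stops cetuximab. A stop before the third cetuximab dose therefore removes that cycle for both drugs, so exclusion depends on the shortfall being measured.
- The nanrilkefusp alfa target does not follow a permitted dose increase, so values above 100% can hide missed doses.
- The overall cetuximab figure has two stated targets and no rule for combining them. Two programmers could report different values for every patient with two or more cycles.

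At stake is a descriptive table that readers use to judge whether the planned dose was delivered.

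**Working it through.** **Inputs.** Nanrilkefusp alfa: 4 doses per 21-day cycle at 9 or 12 µg/kg (SAP 2.1 and Table 1). Cetuximab: 400 mg/m² once, then 250 mg/m², three doses per cycle (Protocol Table 6.1). Definitions: SAP 5.6.1. Cycles are taken as 21 days without delay (assumption).

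**The plan's own figures.** 400 + 250 + 250 = 900 and 3 × 250 = 750 mg/m², as the SAP states. Intended nanrilkefusp alfa intensity is 9 × 4/21 = 1.714 or 12 × 4/21 = 2.286 µg/kg/day.

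**1. Partial last cycle.** Take m fully dosed cycles, then d of 4 nanrilkefusp alfa doses before stopping. For m ≥ 1 the SAP reports 100%. Over started cycles the value is 100 × (4m + d)/(4(m + 1)).

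| m | d = 1 | d = 2 | d = 3 | SAP |
|---|---|---|---|---|
| 0 | 25% | 50% | 75% | no value |
| 1 | 5/8 = 62.5% | 75% | 87.5% | 100% |
| 4 | 17/20 = 85% | 90% | 95% | 100% |

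The first row matters for the ASaT table. The Efficacy population (SAP 3.4) requires all 4 + 3 doses in cycle 1, or exposure to both drugs with cycle 2 started. That nearly matches having a completed cycle 1, so the ASaT dose-intensity summary would cover almost the same patients as the Efficacy one.

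**2. Escalation from 9 to 12 µg/kg.** The target stays at 4 × 9 = 36 µg/kg per cycle.
- Full cycle at 12 µg/kg: 48/36 = 133.3%.
- The same cycle with one of four doses missed: 36/36 = 100%. Against the level assigned for that cycle it is 36/48 = 75%.

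For the overall figure, the timing of escalation matters. Count from day 1 of the last 9 µg/kg patient. That patient's DLT period ends on day 21. Under the staggering rule in Protocol 4.1.1, the 12 µg/kg patients start on days 22, 29 and 30 at the earliest, and the last DLT period ends on day 50. The 9 µg/kg patient's cycle 3 starts on day 43 and cycle 4 on day 64. Without delays, escalation therefore comes at cycle 4 or later.
- Three cycles at 9 and one at 12 µg/kg: (3 × 36 + 48)/(4 × 36) = 108.3%.
- Three cycles at each level: (3 × 36 + 3 × 48)/(6 × 36) = 116.7%.

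Protocol 9.5 limits the reach: "Therefore, 3 to 6 DLT-evaluable patients per dose level will be included in a cohort".

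**3. Overall cetuximab, fully dosed for k cycles.** Actual intensity is (900 + 750(k − 1))/(21k) mg/m²/day.

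| k | Actual | Against 900/21 | Against 750/21 |
|---|---|---|---|
| 2 | 39.286 | 91.7% | 110.0% |
| 4 | 37.500 | 87.5% | 105.0% |
| 8 | 36.607 | 85.4% | 102.5% |

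Neither target alone returns 100% beyond cycle 1. The summed target (900 + 750(k − 1))/(21k) does so for every k. The by-cycle cetuximab figure is correct, because each cycle has its own target.

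**The case against.** The completed-cycle rule is explicit, and the table is computed correctly for what it defines. SAP 5.6.1 also summarises, without that restriction, cycles started, number of doses, duration of exposure, patients with a dose adjustment and cumulative dose. SAP 5.6.3 adds adverse events leading to permanent discontinuation. A patient who stops in cycle 1 is visible there. The compliance measure follows dose changes. Measuring against the initial dose is a definable convention, and escalation is open to few patients, at the investigator's discretion. The SAP nowhere says that one cetuximab target applies to every cycle, so the percentages in step 3 are possible readings, not stated results.

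Much of this stands. It makes the matter one of descriptive reporting, and the cetuximab point a gap in specification. It does not remove the asymmetry. The unrestricted summaries are not expressed against intended dose, and compliance is calculated per dosing and only listed. Stating a rule openly does not stop it from leaving out the cycle in which delivery failed.

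Counting all started cycles has a weakness of its own. SAP 5.6.1 defines a started cycle separately for each drug, and Protocol 7.1 lets nanrilkefusp alfa continue after cetuximab stops in some cases. Per-drug counting would then miss the lost cetuximab cycles, so the definition has to refer to either drug.

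**Conclusion.** The concern holds in a limited form. SAP 5.6.1 can overstate overall relative dose intensity for nanrilkefusp alfa and leaves the overall cetuximab figure undefined. For one full cycle plus 1 of 4 doses the gap is 37.5 percentage points (100% against 62.5%); after four full cycles it is 5 to 15 points. Escalated cycles score 133%, or 100% with a dose missed, in patients of the 9 µg/kg cohort only. The figures assume undelayed 21-day cycles and full dosing except where stated. The direction is not fixed: dropping a last cycle that was better delivered than earlier ones would not inflate the result.

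Four stronger readings are tempting, and the documents do not support them.
- That the formulas give wrong percentages for everyone. For a patient on a constant dose whose started cycles all count as completed, the nanrilkefusp alfa figure is correct.
- That relative dose intensity is the trial's RP2D or tolerability measure. Protocol section 3 ties RP2D to DLTs, and safety and tolerability to adverse events, laboratory findings, vital signs and ECG.
- That escalation after two cycles, with four more at 12 µg/kg, gives 122%. The undelayed sequence does not allow escalation that early.
- That the administered-dose formula "2 x Total volume administered) / patient weight" is off by a factor of 1000. This needs volume to be recorded in mL, which neither document says; the SAP labels the result µg/kg.

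ORR, the futility rule and the sample size are unaffected.

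**What to change.** In SAP 5.6.1, define overall relative dose intensity for each drug as

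100 × (actual dose over all cycles in which either drug was given / total days of those cycles, last cycle = 21 days) / (sum of intended dose for those cycles / (21 × number of those cycles)).

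- Intended cetuximab: 900 mg/m² for cycle 1 and 750 mg/m² for each later cycle.
- Intended nanrilkefusp alfa: the assigned level × 4, updated from the cycle of an escalation permitted under Protocol 4.1.1, and not lowered for toxicity reductions. The by-cycle figure should use the same target.
- Keep the completed-cycle version as a supportive table.

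A fully dosed, undelayed patient then scores 100% on either drug. Patients who stop in cycle 1 have a value in the ASaT table.

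The cost is SAP wording and programming on data already collected. Reported values will fall somewhat, and a last cycle cut short by progression will also count as dose loss. The table should say so in a footnote.
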